the attending psychiatrist (n=89), distance (n=30), and prolonged hospitalization due to receipt of electroconvulsive therapy (n=30). Participation in the intervention exceeded our target thresholds with 95 % of intervention participants completing a meeting with the peer mentor prior to discharge (target 80%) and a mean completion of 5.6 (SD 4.8) peer encounters over 3 months (target mean of 4). The most common reason for not completing any encounters after discharge (n=9) was feeling overwhelmed or too busy; participants were offered to switch to a new peer mentor, but none chose this option, suggesting the reasons for poor engagement were not specific to the individual peer mentors. Excluding participants pending follow-up (pilot study is still collecting follow-up data), 79% (49 of 62) have completed the 3-month assessments and 80% (28 of 35) have completed the 6-month study assessments. Exceeding our target of 60 for enrollment and target of 75% for follow-up assessments demonstrates feasibility to proceed to a larger-scale trial.

Supervision, fidelity, and refinement of the intervention. Fidelity to the intervention, including suicide safety protocols, was maintained by weekly group supervision meetings consisting of the peer mentors and the principal investigator (a psychiatrist) or a co-investigator psychiatrist or psychologist. Each participant encounter was discussed, training materials and intervention protocols were reviewed, and audio-recordings of individual sessions were presented for feedback. Following the initial phases of the trial, the structure of the intervention session content was refined to facilitate fidelity by establishing a consistent format across content areas. The format used the mnemonic "ILSM" which stands for "Invite, Learn, Share, Motivate", and a semi-structured conversation guide was created for each content domain in this format (Other Attachment IIB). The format incorporates motivational interviewing concepts and techniques—encouraging peers to first understand the participant's experiences and ideas for change—

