New approaches to suicide prevention are needed to meet the rising tide of suicide deaths in the U.S. Peer mentorship represents a novel approach to reducing suicide risk by addressing poor belongingness and hopelessness, two risk factors for suicide supported by theory, evidence, and advocates. This study of peer mentorship will be the first effectiveness trial of a peer-delivered intervention designed to reduce suicide attempts and suicidal ideation. This study advances peer support research by the inclusion of intermediate targets in the intervention design and assessment of potential mediators. A safe and effective peer-based intervention to prevent suicide attempts could achieve wide scale implementation due to a growing, professionalized, and integrated peer specialist workforce that increasingly supports high-risk individuals. The hybrid effectiveness-implementation design used in this study is an innovative approach to reducing delays in translating evidence from clinical trials into practice.

A major limitation to clinical trial research is that wide spread implementation of effective interventions may take decades or never occurs after publication of the trial results. (13) Hybrid effectiveness-implementation trial designs are intended to address this problem by studying the barriers and strategies for future implementation simultaneous to the determination of effectiveness. (14) Even if the specific intervention proves not to be effective, assessment of stakeholder experiences with the intervention may provide explanations for the null findings, guide future research, and inform ongoing initiatives to increase peer involvement in suicide prevention.

STUDY DESIGN

We will conduct a single-blind randomized controlled trial of the PREVAIL peer mentorship for suicide prevention intervention compared to enhanced usual care among 490 participants at high-risk for suicide recruited from inpatient psychiatric units.

Study Flow

STUDY PROCEDURES

Schedule of Activities

	Pre-screening (Pre- enrollment)	Enrollment - Week 1, Day 1	Baseline - Week 1, Day 4	Intervention - Week 1	Intervention - Week 2	Intervention - Week 3	Intervention - Week 4	Intervention - Week 5	Intervention - Week 6	Intervention - Week 7	Intervention - Week 8	Intervention - Week 9	Intervention - Week 10	Intervention - Week 11	Intervention - Week 12	Intervention - Weeks 12-16	Intervention - Weeks 16-23	Intervention - Week 24	Withdrawal
Review eligibility	X																		

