Informed consent – study staff will obtain informed consent from interested individuals before they are discharged from the inpatient unit. The study staff member will review all study activities, emphasize that participation is voluntary, discuss potential risks and benefits of participating, and review the participant's responsibilities. An individual is considered enrolled once informed consent has been provided.

Post-consent activities and outcomes assessments

Outcome assessments are performed at three time points across an individual's participation in the study: baseline (while the participant is admitted to the inpatient unit), 3 months, and 6 months from their enrollment in the study.

Beck Hopelessness Scale, Beck Scale for Suicidal Ideation, Columbia Suicide Severity Rating Scale, State Hope Scale, Interpersonal Needs Questionnaire, Multidimensional Scale of Perceived Social Support, Meaning of Life Questionnaire, Single-Item Self Rating of Medication Adherence, NIH Adult Toolbox Social Relationship Scales, Patient Health Questionnaire (PHQ-9), Quality of Life Enjoyment and Satisfaction Questionnaire Short Form, Self-Efficacy to Avoid Suicidal Action Scale, Working Alliance Inventory – Client, Short Form 12, and health service utilization inventory (lifetime or 3 month interval) – these will be collected via self-reported measures at baseline, 3 month, and 6 month assessments.

Randomization and Blinding

Randomization will be conducted using a minimization algorithm implemented by the University of Michigan's Consulting for Statistics, Computing & Analytics Research (CSCAR) center.(80) The two variables included in the minimization are gender and whether the participant made a suicide attempt immediately prior to hospital admission. These variables were chosen to avoid the potential confounding that could arise if by chance these variables were not equally distributed during random assortment.(81) Randomization will be stratified by study site. After a participant has completed consent procedures and the baseline assessment, a research assistant will access the CSCAR web application, input the two variables, and receive the allocation assignment.

All follow-up assessments will be completed by a separate research assistant who will be blinded to study arm assignment.

Control & Experimental Interventions

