Once study arm is ascertained, the study team will commence with study intervention activities. The study staff member will schedule the participant's 3 month assessment and provide them with a copy of the Informed Consent Document, and then either (1) the baseline visit will be complete, or (2) the study staff member will instruct the participant to select a peer mentor from a list of short written descriptions of peer mentors currently available to accept a new patient, and will coordinate an initial meeting between the participant and their selected peer mentor to take place on the inpatient unit before the participant is discharged.

Outcome Assessments

The 3 and 6 month outcome assessments should occur within the windows listed on the schedule of activities, through in-person meetings with separate research staff blinded to study arm assignment. In cases where in-person attendance is not feasible, the measures can be completed over the phone or internet, though in these cases the participant's location and availability of an emergency contact person will first be confirmed in the event of acute suicidality. If a participant fails to complete an assessment within the prescribed window, that assessment will be documented as incomplete.

Withdrawal

If participants withdraw or decline to finish the peer mentorship intervention, every effort will be made to gather primary outcome data (Columbia Suicide Severity Rating Scale, Beck Scale for Suicide Ideation). These surveys may be done in person or over the phone.

In the event that a participant withdraws before completing all study activities, staff will administer a brief semi-structured Early Withdrawal Interview to gather feedback on the participant's experience with study activities.

Retention

Research staff may encounter difficulty contacting participants for the purpose of completing study activities. In order to minimize attrition and maintain high follow-up completion rates, staff will collect thorough contact information at the time of enrollment by having each participant complete a Participant Locator Form.

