Peer mentors will be provided study cell phones to contact participants. These cell phones will be password encrypted, and will be stored in a combination lockbox when not in use. Peer mentors may use these cell phones to text participants in order to schedule meetings if they are unable to reach them by phone call. Peer mentors will keep

these study cell phones turned off outside of business hours when they are not meeting with a participant, and will maintain an outgoing voicemail greeting that provides the National Suicide Prevention Lifeline phone number.

Peer mentors may email participants for the purpose of scheduling mentorship sessions. Peers will use email for scheduling only if the participant has no working phone available where they can be reached. All email communications from peer mentors will be sent from Level 2 email accounts.

SELECTION AND ENROLLMENT OF PARTICIPANTS

Inclusion Criteria

The goal of the study inclusion and exclusion criteria is to identify a broadly representative sample of inpatient psychiatric patients at high risk for suicide based on a suicide attempt or suicidal ideation prior to admission. Including only those with a suicide attempt would limit the generalizability of the intervention. Recruitment from inpatient units facilitates the initial in-person peer support contact in a safe setting and ensures some intervention has taken place prior to when patients are at maximal risk immediately following discharge. (77)

Patients will be eligible for the study if they: 1) are age 18 years or older, 2) are currently admitted to an inpatient psychiatric unit and have medical record documentation of suicidal ideation or suicide attempt at the time of admission, 3) have a Beck Suicide Scale score of 5 or higher for the 1-week period prior to admission, 4) are fluent in English, and 5) are able to be reached reliably by telephone. The age and language criteria are necessary because peer mentors will be English-speaking adults.

Exclusion Criteria

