Effects over time: We will also assess the intervention effects over time using longitudinal data for both suicidal ideation and suicide attempt. For suicidal ideation, we will use a linear mixed-effects model with ideation assessed at baseline, 3 months, and 6 months. The model will allow the full use of all observed data despite missing outcomes at one or two assessment times and will give unbiased estimates as long as the missingness does not depend on the unobserved missing data (missing at random). For suicide attempt, we will use a generalized linear mixed-effects model with logit link for any suicide attempt in the prior 3 months as a binary response variable assessed at 3 and 6 months. These models will include participant as random intercepts to take into account the correlation of data within person over time. The models will allow estimation of the time-averaged effect of the intervention if the response to the intervention is immediate and lasting, or estimate the differential effect of the intervention over time if a significant interaction between time and intervention is found, such as different trends between the study groups. Whether we compare the time-averaged effects or the rates of changes between two groups, we will be guided by careful graphical exploration of the longitudinal data over time between the two groups. For example, if we find decreasing BSI scores from baseline to 3 months in both groups, but with a larger decrease in the intervention group, this will be modeled with interaction terms of time indicators for 3 and 6 months each by intervention group. The coefficients from the interaction terms of the BSI model will then allow testing for the between-arm difference in decrease in BSI from baseline to 3 months and baseline to 6 months. Similarly, the interaction term of the suicide attempt model will allow testing if the odds ratio of suicide attempt associated with the intervention differs from month 3 to month 6.

Secondary Outcomes

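### The longitudinal attempt model uses a fixed 3-month look-back that does not fit a first follow-up allowed anywhere in Weeks 12-16, so its month 3 versus month 6 comparison depends partly on visit timing

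*Combined protocol and SAP*

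**What the plan says.** The Statistical Analyses Plan, under Effects over time, fits a mixed model with logit link to "any suicide attempt in the prior 3 months as a binary response variable assessed at 3 and 6 months". The time-by-arm interaction is meant to show whether the intervention odds ratio changes between the two visits.

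In the Schedule of Activities, the Columbia scale's follow-up marks fall under "Intervention - Weeks 12-16" and "Intervention - Week 24". The Outcome Assessments section ties the visits to that table: "The 3 and 6 month outcome assessments should occur within the windows listed on the schedule of activities". The clock is set under Post-consent activities, where visits are timed at "3 months, and 6 months from their enrollment in the study". The same section lists the "health service utilization inventory (lifetime or 3 month interval". This inventory is one of two triggers for the medical-record search behind the first secondary outcome; the Columbia scale is the other.

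The primary attempt outcome is separate. It is any actual, aborted or interrupted attempt over the 6 months after enrollment, analyzed by a single logistic regression. No recall period is given for it, and no rule says how the two visits combine. The documents do not print the recall wording of the follow-up Columbia scale.

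**The concern.** A look-back of fixed length, applied at a visit that can move by about four weeks, cannot divide 24 weeks into two adjoining periods. An early attempt can fall in neither period, and an attempt around Weeks 11-16 can fall in both. For an early attender, an attempt from before enrollment can fall in the first period. The month 3 versus month 6 interaction then mixes any change in the intervention effect with differences in visit timing.

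The uncovered time is also time the design cares about. The Inclusion Criteria section justifies inpatient recruitment because it "ensures some intervention has taken place prior to when patients are at maximal risk immediately following discharge". Participants normally enroll before discharge, or up to one week after it, so the uncovered days lie at or near that period.

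Missed visits raise a related question. In the pilot, "79% (49 of 62) have completed the 3-month assessments", so 13 of 62 (21%) had not. If such a participant returns at Week 24 and is asked only about 3 months, everything before about Week 11 is lost.

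**Working it through.** **Plan's own figure.** The plan states 84% power for 22% versus 36% with 184 per group at two-sided 0.05. The two-proportion formula with pooled null variance gives 84.4%, so the figure reproduces. The plan gives no figure for how much follow-up time the attempt question covers.

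**Inputs.** First follow-up in Weeks 12-16 and second at Week 24 (Schedule of Activities). Look-back of 3 months, taken as 91 days (Effects over time). Week w ends on day 7w, counted from enrollment. Pilot attempt rate 24% at 3 months (Preliminary Studies, Outcomes and safety).

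**Coverage.** Let V be the day of the 3-month visit, with the 6-month visit on day 168.
- Start of first look-back = V - 91. A positive value is uncovered time; a negative value is time before enrollment.
- Start of second look-back = 168 - 91 = day 77.
- Overlap = V - 77.

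| 3-month visit | Uncovered after enrollment | Reaches before enrollment | In both periods |
|---|---|---|---|
| Day 84 (end of Week 12) | 0 | 7 days | 7 days |
| Day 91 (end of Week 13) | 0 | 0 | 14 days |
| Day 106 (start of Week 16) | 15 days | 0 | 29 days |
| Day 112 (end of Week 16) | 21 days | 0 | 35 days |

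A visit on day 78 (start of Week 12) reaches 13 days before enrollment. Whether the participant attempted suicide just before admission is a minimization variable, so such attempts are expected in this sample and could be counted as outcomes.

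For the end of Week 16, reading 3 months as 84 to 92 days moves the gap from 28 to 20 days and the overlap from 28 to 36 days.

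**Missed 3-month visit.** With a 91-day look-back at day 168, days 0-77 are unobserved: 77/168 = 46% of follow-up.

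**Illustrative size, if the primary outcome uses the same items.** Assume a constant weekly hazard h = -ln(0.76)/13 = 0.0211.
- First attempt within the gap: 1 - exp(-0.0211k) for k = 1, 2, 3 weeks gives 2.1%, 4.1% and 6.1% for visits at the end of Weeks 14, 15 and 16.
- Not all of these are misclassified, because a later attempt would still be reported. For a Week 16 attender seen at both visits: 6.1% x exp(-0.0211 x 21) = 6.1% x 0.642 = 3.9%.
- If the hazard in the first 4 weeks is twice the later hazard c (17c = 13 x 0.0211, so c = 0.0161), the first-attempt share at Week 16 is 1 - exp(-6c) = 9.2%. The misclassified share is 9.2% x exp(-22c), about 6.5%.
- For a participant seen only at Week 24: [1 - exp(-0.0211 x 11)] x exp(-0.0211 x 13) = 20.7% x 0.76 = 15.7%.

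The constant hazard is only a device. Carried to 24 weeks it gives 1 - exp(-0.0211 x 24), about 40%, which is above both planning rates.

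**Power, on the same condition.** If 5% or 10% of participants with an attempt were missed equally in both arms, power would fall from 84.4% to 81.7% or 78.8%. The documents give no basis for choosing between these values.

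**The case against.** The strongest reply is that the look-back belongs to the response variable of a supplementary model, and that the phrase may be shorthand for the interval between assessments. Other text points to recall since enrollment: the pilot Columbia result is reported for attempts after enrollment, and the primary hypothesis covers the 6 months following enrollment. This stands, and it rules out several stronger readings that a reader might infer.

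- *That participants are only ever asked about 3 months, so the trial cannot see early attempts.* The follow-up recall wording is not in the documents. The entry for the service inventory is a label in a list and does not settle it either.
- *That the primary outcome has the gap however it is defined.* If the scale asks since enrollment and then since the last assessment, there is no gap.
- *That double counting inflates the primary outcome.* An attempt reported twice cannot change a single yes/no variable over 6 months.
- *That the lost weeks are the stated period of maximal risk.* The protocol ties that risk to discharge and gives no duration.
- *That the comparison between arms is biased.* The windows are the same in both arms and follow-up assessors are blinded, so no such bias is shown.

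Late visits may also be uncommon. Visits are scheduled ahead with repeated reminders, but no distribution of visit dates is given.

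The reply does not remove the problem in the longitudinal model. Followed as written, its rule gives misaligned periods. If the instrument does ask since enrollment, the model's definition conflicts with the instrument and still needs correcting.

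**Conclusion.** The concern holds for the longitudinal attempt model and should be fixed. With a 91-day look-back, the two periods leave up to 21 days after enrollment uncovered, share up to 35 days with a day-168 visit, or begin 7 to 13 days before enrollment for a Week 12 visit. The test of a changing odds ratio is therefore partly a function of visit dates.

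For the primary any-attempt outcome the concern is conditional. It applies only if that outcome is assembled from the same 3-month items. Early attempts would then be lost for late attenders, and about Weeks 0-11 would be lost for anyone who missed the 3-month visit and returned at Week 24. The 3.9% figure rests on a constant hazard, a visit at the end of Week 16 and attendance at both visits. The gap is near zero at Week 13, and no trial-wide loss can be calculated without visit dates.

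**What to change.** Under Effects over time, replace the 3-month look-back with two periods defined by date: randomization to Week 12, and Week 12 to Week 24. Alternatively, define them by recall: *since randomization* at the first follow-up, and *since the last completed assessment, or since randomization if there was none* at the second. Use that recall for both the Columbia scale and the Health Services Inventory, and record the date of each attempt. Derive the primary any-attempt outcome from attempts dated after randomization. This excludes the index attempt and makes clear what is known for someone who missed the 3-month visit.

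The cost is one recall stem, a date field and one sentence in the analysis plan. Participants seen late, or who missed the first visit, face a somewhat longer recall.

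The documents do not say whether follow-up is still running. Changing the stem midway would mix two recall definitions within one outcome. If data are already collected, state the recall wording that was used and redefine the periods from the recorded dates.

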Based on estimates from the participating sites and pilot study results, we anticipate 480 (60% of 800) patients will be admitted to UM per year with medical record documentation of suicidal ideation or a suicide attempt. We anticipate that the number of patients admitted to Henry Ford Macomb and Wyandotte with medical record documentation of suicidal ideation or a suicide attempt will be similar to that seen at the previous Henry Ford Kingswood site (n=720 per year, or 60% of 1200). Of these, we estimate 60% will not meet eligibility criteria and 22% will refuse, such that 216 could be recruited per year. Enrollment of 490 participants during 3 years of recruitment is therefore feasible. The PI of the study ([name]) will oversee recruitment via weekly calls with HF site PI ([name]) and coordinators from both institutions. Informed consent will be obtained from all participants (see Protection of Human Subjects). Baseline measures (see D2j) will be completed at the time of enrollment, prior to study arm assignment.

Telephonic Screening and Recruitment During COVID-19 Pandemic

Due to health concerns and limitations imposed on in-person research activities during the COVID-19 pandemic, screening and recruitment of subjects will take place telephonically during this time. Potentially eligible patients will be identified via chart review, and approved for recruitment by their attending provider as usual. Research staff will obtain eligible and approved patient(s)' on-unit cell phone number from inpatient unit staff and call the patient(s) to pitch the study using an oral script. Interested patients will receive a study packet from unit staff that includes (1) Consent to be Screened, (2) Consent to be a Part of a Research Study, (3) a printed copy of study measures, (4) printed copies of peer mentor bios, and (5) a study timeline handout that includes study team contact information. Patients will not have access to smart phones, tablets, or private computers on the inpatient units; therefore, all enrollment activities must take place over the phone, and a waiver of documentation of informed consent must be utilized for these enrollments. Subjects will keep the paper copies of consent forms for their records.

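### The longitudinal ideation model counts pre-allocation baseline as an outcome, so in its no-interaction form the time-averaged effect, on its natural reading, is diluted by at least a third

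*Combined protocol and SAP*

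**What the plan says.** Under Data Analysis, Effects over time, the plan states for ideation: "we will use a linear mixed-effects model with ideation assessed at baseline, 3 months, and 6 months". The covariance structure is a random intercept: "These models will include participant as random intercepts to take into account the correlation of data within person over time". Under Enrollment, baseline measures "will be completed at the time of enrollment, prior to study arm assignment".

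Two summaries are then offered. The first is "The models will allow estimation of the time-averaged effect of the intervention if the response to the intervention is immediate and lasting". The second is "or estimate the differential effect of the intervention over time if a significant interaction between time and intervention is found". On choosing between them, the plan says "we will be guided by careful graphical exploration of the longitudinal data over time between the two groups". Its worked example is a larger fall in ideation from baseline to 3 months in the intervention arm, and "this will be modeled with interaction terms of time indicators for 3 and 6 months each by intervention group".

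The companion attempt model has no baseline response. It uses "any suicide attempt in the prior 3 months as a binary response variable assessed at 3 and 6 months".

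No equation is given for the time-averaged version. Nothing says that baseline is left out of the average, constrained equal between arms, or moved to the covariates. The primary ideation analysis is a separate 6-month multiple regression (Bivariate/Multivariate Analyses). Approach to Missing Data relies on the mixed model to give an unbiased intervention effect when data are missing at random.

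**The concern.** The plan presents the time-averaged effect as the alternative to a model with a time-by-arm interaction. In a model with three response visits and no interaction, the only treatment parameter is the arm term, which averages the arm difference over all three. One of those differences is zero in expectation because it was measured before allocation. A benefit that appears by 3 months and persists to 6 months is then averaged with a zero.

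Measured from a pre-treatment baseline, an immediate and lasting effect is also a time-by-arm interaction. The no-interaction average is therefore diluted under the very condition the plan attaches to it.

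Three things are at stake. The longitudinal estimate could look clearly smaller than the 6-month regression for no clinical reason. The analysis would lose power. And the model relied on as the safeguard against missing data would, in this form, be biased toward zero even with no data missing.

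**Working it through.** **Inputs from the documents.** 490 enrolled, 25% dropout, 184 per arm analysed, d = 0.34, two-sided 0.05 (Sample Size); pilot BSS SDs of 7.6 at baseline and 7.7 at 3 months (Outcomes and safety). **Assumed, because not given:** ICC 0 to 0.8, the timing of losses, and the correlations named below.

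**1. The plan's own figure.** SE = √(2/184) = 0.1043; 0.34/0.1043 = 3.26; 3.26 − 1.96 = 1.30; power = 0.903. The stated 90% reproduces. It belongs to a two-group comparison at one visit; the plan states no power for the mixed model.

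**2. Complete data, no interaction.** True arm differences are (0, D, D). With a random intercept, all visits of a complete case get equal weight, so the arm term estimates (0 + D + D)/3 = 0.667D, which is 33% too small at any ICC.

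**3. With 25% dropout.** The weight of a participant with m visits is m/(1 + (m − 1)ρ), where ρ is the ICC.

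- *All 25% miss both follow-ups:* the estimate is 0.75·2/(1+2ρ) divided by [0.75·3/(1+2ρ) + 0.25], which simplifies to 1.5/(2.5 + 0.5ρ) times D.
- *12.5% lost before month 3 and a further 12.5% before month 6:* the numerator is 1.5/(1+2ρ) + 0.125/(1+ρ); the denominator is 2.25/(1+2ρ) + 0.25/(1+ρ) + 0.125.

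| ICC | All lost before month 3 | Staggered loss |
|---|---|---|
| 0 | 0.600D | 0.619D |
| 0.5 | 0.545D | 0.588D |
| 0.8 | 0.517D | 0.572D |

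The range is 0.52D to 0.62D, or 38% to 48% too small.

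**4. Check by model fits.** In 60 simulated REML fits (490 participants, 25% with no follow-up, ICC 0.4, true effect −3.4), the arm main effect averaged −2.01. The arm-by-post-baseline term averaged −3.56 with baseline means constrained equal and −3.54 without. The ratio 2.01/3.56 = 0.565 agrees with the formula, 1.5/2.7 = 0.556.

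**5. Power cost of the no-interaction form.** Take 184 complete per arm, d = 0.34, ICC 0.5.

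- *Three-visit average:* effect 0.227, variance (1 + 2·0.5)/3 = 0.667, power 0.76.
- *Average of 3 and 6 months:* effect 0.34, variance (1 + 0.5)/2 = 0.75, power 0.96.

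**6. The interaction branch.** In the fits of step 4 its coefficients averaged −3.55 and −3.53, so there is no dilution. It does carry the sampling noise of an unconstrained baseline difference. For the 6-month contrast with baseline correlation r, the variance factor is 2(1 − r) unconstrained and 1 − r² with a common baseline. With 184 completers per arm and d = 0.34:

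| r | Unconstrained | Common baseline |
|---|---|---|
| 0.2 | 0.73 | 0.91 |
| 0.3 | 0.79 | 0.93 |
| 0.5 | 0.90 | 0.96 |

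A simulation with 245 randomized per arm, an unstructured covariance, follow-up losses of 21% and 25%, r of 0.2 to 0.3, and correlation 0.6 between follow-ups gave 0.80 to 0.82 against 0.94 to 0.95.

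**7. How often the diluted branch would be used.** At the design effect (0.34 × 7.7 = 2.62 points), simulated trials with baseline correlations of 0.2 to 0.4 had a non-significant interaction test in about 5% to 16% of runs. In one set of these runs, with 21% and 25% missing, the arm term in the non-significant trials averaged 1.45 to 1.50, or 55% to 57% of 2.62. At a true effect of 1.9 points and r = 0.3, the test was non-significant in about 33% of runs, and there the arm term averaged 1.01 (53%).

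**The case against.** The diluted estimator is a reading of the text, not a written specification. The preceding section ties immediate effects to 3 months and lasting effects to 6 months, and the sentence about the time-averaged effect covers both models, one of which has only those two visits. An analyst could take it to mean an average over 3 and 6 months, which would be unbiased. This stands: the dilution is conditional on the reading.

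The plan's example also sends a larger fall from baseline to the interaction terms, which are undiluted. Under the stated significance rule, most trials at the design effect would report those terms. This stands too. A reader might infer that the plan's longitudinal effect is always understated by a third or more, or that fixing the choice of model in advance would not help. The documents support neither: if the interaction model is the one fixed, attenuation is zero.

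A reader might also infer that the trial's main ideation result or its power is compromised. It is not. The model is supplementary, the primary analysis is the 6-month regression, and similar 3-month analyses are planned.

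Finally, the power gap in step 6 compares two unbiased contrasts, so it is a matter of efficiency and not an error.

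What remains is that the plan's only description of the time-averaged effect sets it against the interaction model and nowhere removes baseline. The choice between the two also depends on a significance test and on graphs by arm.

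**Conclusion.** The point holds for one branch of a supplementary analysis. If the no-interaction branch is used and the time-averaged effect is the arm term over three visits, a constant benefit is estimated at two thirds of its size with complete data. That figure needs no assumption about the ICC. With 25% dropout the estimate is about 0.52 to 0.62 of the true size, which does depend on the assumed ICC (0 to 0.8) and loss pattern. Under the significance rule this branch would be reached in roughly 5% to 16% of trials at the design effect and more often for smaller effects. Because graphs also guide the choice, the exact frequency cannot be known.

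The interaction branch is unbiased but loses power when the baseline correlation is low: about 0.73 to 0.82 against 0.91 to 0.95 at an assumed 0.2 to 0.3. The gap narrows as the correlation rises.

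The primary 6-month regression, the attempt model, and the stated 90% and 84% powers are untouched. The change is worth making because it costs almost nothing and because the missing-data section relies on this model.

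**What to change.** In Effects over time, rewrite the ideation model as follows:

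- Keep baseline, 3 and 6 months as responses, but prespecify a common baseline mean for the two arms: no arm main effect, with arm-by-3-month and arm-by-6-month terms retained.
- Define the time-averaged ideation effect as the mean of those two terms.
- Report both visit-specific terms in every case, whatever the interaction test or the graphs show.

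This removes the diluted branch and improves on the precision of the unconstrained contrast. It costs SAP wording only, with the same data and software. The attempt model needs no corresponding change, since it has no baseline response.
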